12.2.2. Derived and transformed data

Serology data

- The cut-off value for M72-specific antibody concentrations is 2.8 EU/mL.
- The assay cut-off is the value below which there is no quantifiable result available. For an assay with a specific 'cut-off', numerical immunogenicity results are derived from a character field (rawres):
 - If rawres is 'NEG' or '-' or '(-)', numeric result = cut-off/2,
 - if rawres is 'POS' or '+' or '(+)', numeric result = cut-off,

- if rawres is ‘< value’ and value \leq cut-off, numeric result = cut-off/2,
- if rawres is ‘< value’ and value $>$ cut-off, numeric result = value,
- If rawres is ‘> value’ and value $<$ cut-off, numeric result = cut-off/2,
- if rawres is ‘> value’ and value \geq cut-off, numeric result = value,
- if rawres is ‘ \leq value’ or ‘ \geq value’ and value $<$ cut-off, numeric result = cut-off/2,
- if rawres is ‘ \leq value’ or ‘ \geq value’ and value \geq cut-off, numeric result = value,
- if rawres is a value $<$ cut-off, numeric result = cut-off/2,
- if rawres is a value \geq cut-off, numeric result = rawres,
- if rawres is a value \geq cut-off, numeric result = rawres,
- otherwise the numeric result is left blank.

- A seronegative subject is a subject whose antibody concentration is below the cut-off value.
- A seropositive subject is a subject whose antibody concentration is greater than or equal to the cut-off value.
- The seropositivity rate is defined as the percentage of seropositive subjects.
- The GMC calculations will be performed by taking the anti-log of the mean of the log10 concentration transformations. Antibody concentrations below the cut-off of the assay will be given an arbitrary value of half the cut-off for the purpose of GMC calculation.

ICS data (CD4+/CD8+ T-cells per 10^6 cells expressing at least two different immune markers [IFN- γ and/or TNF- α and/or IL-2 and/or CD40L])

- To compute the frequency of M72-specific CD4+ T-cells expressing at least 2 immune markers among IL-2, IFN- γ , TNF- α and CD40-L, there are two methods:

Method 1:

- Background reduction: stimulated minus background value. If the difference is < 0 , then the value 1 was given.
- Sum all the combinations with at least 2 immune markers.

Method 2:

- Sum of all the combinations with at least 2 immune markers for the stimulated frequencies.
- Sum of all the combinations with at least 2 immune markers for the background frequencies.
- Stimulated minus background value. If the difference is < 0 , then the value 1 was given.

The method 2 will be used for the analysis of CD4+ T-cells polypositives.

- ICS data will be expressed as M72-specific CD4+/CD8+ T-cells per million CD4+ or CD8+ T-cells, respectively.
- A responder will be defined as a subject:
 - Whose post-vaccination frequency of cells is higher than the 95th percentile of pre-vaccination frequencies of all subjects;
 - Whose post-vaccination frequency of cells is at least 2 times/at least 3 times/at least 4 times his/her frequency of cells at pre-vaccination.

ICS data (CD4+/CD8+ T-cells expressing any combination of immune markers among IFN- γ , TNF- α , IL-2 and CD40L])

The following steps will be performed:

- Subtraction of background value for each subject,
- Replacement of negative or null value by 1,
- Calculation of new combinations of immune markers without the CD40L marker:
CD40L was included in the ICS assay but the signal contributed by CD40L was not taken into account in this analysis.

For example: IL-2 single positive = (IL-2⁺) + (IL-2⁺/CD40L⁺)

- Calculation of M72-specific CD4+/CD8+ T-cells expressing at least IL-2 or at least IFN- γ or at least TNF- α :

The frequency of M72-specific CD4+/CD8+ T-cells expressing at least a given immune marker represents the sum of single, double, triple, quadruple positive CD4+/CD8+ T-cells for that given immune markers

For example: Total IL2 = (IL2⁺) + (TNF+/IL2⁺) + (IFN+/IL2⁺) + (IL2⁺/CD40L⁺) + (IL2⁺/TNF+/IFN⁺) + (IL2⁺/CD40L+/IFN⁺) + (IL2⁺/TNF+/CD40L⁺) + (IL2⁺/TNF+/IFN+/CD40L⁺).

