12.2. Immunogenicity

12.2.1. Handling of missing data

For a given subject and a given immunogenicity measurement, missing or non-evaluable measurements will not be replaced.

Therefore, an analysis will exclude subjects with missing or non-evaluable measurements.

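### SAP 12.2.2 counts a serology result as seropositive when it is known only to lie below a bound above the cut-off; if such results occur, seropositivity and GMC can be overstated

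*SAP*

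**What the plan says.** SAP 12.2.2 (serology data) fixes the threshold: "The cut-off value for M72-specific antibody concentrations is 2.8 EU/mL". It also says what the threshold means: "The assay cut-off is the value below which there is no quantifiable result available". A list then converts raw result strings to numbers. The lines that matter here are:

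- '<' with a bound at or below the cut-off becomes half the cut-off, 1.4 EU/mL.
- '<' with a bound above the cut-off: "if rawres is ‘< value’ and value $>$ cut-off, numeric result = value".
- '≤' with a bound at or above the cut-off also becomes the bound.
- In the other direction: "If rawres is ‘> value’ and value $<$ cut-off, numeric result = cut-off/2". '≥' with a bound below the cut-off is handled the same way.

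The numeric result then drives both summaries. For serostatus: "A seropositive subject is a subject whose antibody concentration is greater than or equal to the cut-off value", and "The seropositivity rate is defined as the percentage of seropositive subjects". For the GMC: "Antibody concentrations below the cut-off of the assay will be given an arbitrary value of half the cut-off for the purpose of GMC calculation".

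SAP 12.2.1 leaves missing or non-evaluable immunogenicity measurements unreplaced and adds: "Therefore, an analysis will exclude subjects with missing or non-evaluable measurements". It does not say whether a censored result that cannot settle serostatus is non-evaluable. The plan gives no retest rule, count or sensitivity analysis for such results.

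**The concern.** A result of '<10' says only that the titre is somewhere below 10 EU/mL. The rule stores the top of that range as if measured, and the seropositivity definition then calls the subject positive. The less the assay says about a low sample, the more positive the subject becomes: '<2.8' is negative, while '<28' is positive with a stored value of 28.

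M72-specific antibody levels and seropositivity are named secondary endpoints (SAP 4.2). SAP 11.9.3.3 tabulates GMCs, seropositivity rates and geometric mean post/pre ratios. Results reported as an upper limit are most plausible in low samples, that is at Day 0 and in the placebo group. There the rule would raise the seropositivity rate and the GMC, and a raised Day 0 value would lower the post/pre ratio.

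**Working it through.** There is no figure in the plan to reproduce. The check applies the plan's rules to test strings and then sizes the effect.

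**Inputs from the documents.** Cut-off 2.8 EU/mL, half of it 1.4 (SAP 12.2.2). About 225 subjects per group in the safety and immune sub-cohort (protocol 6.2.3, Table 5).

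**Assumed inputs.** The share of affected samples (1%, 5%, 10%) and the stated bound (5.6, 14 or 28 EU/mL, i.e. 2, 5 or 10 times the cut-off). The documents give neither.

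**Step 1: what the rules return.**

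| Raw result | Stored value | Serostatus |
|---|---|---|
| < 2.8 | 1.4 | negative |
| < 2.81 | 2.81 | positive |
| < 5.6 | 5.6 | positive |
| < 28 | 28 | positive |
| ≤ 2.8 | 2.8 | positive |
| > 2.7 | 1.4 | negative |

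For a '<' result with bound v above the cut-off, the SAP would assign the true titre either 1.4 or a number below v. The stored v exceeds both. This rule alone can therefore only raise the GMC and can never lower the seropositivity rate.

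**Step 2: upper limits on size.** Let k of n = 225 results be affected and all truly below the cut-off.

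- Overstatement of seropositivity = k/n.
- GMC factor = (v/1.4)^(k/n), whatever the other results in the group are.

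| Assumed share | k | Seropositivity | GMC, v = 5.6 | v = 14 | v = 28 |
|---|---|---|---|---|---|
| 1% | 2 | +0.9 points | 1.012 | 1.021 | 1.027 |
| 5% | 11 | +4.9 points | 1.070 | 1.119 | 1.158 |
| 10% | 22 | +9.8 points | 1.145 | 1.253 | 1.340 |

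The 95% Clopper-Pearson interval does not protect against this. With nobody truly positive, 0/225 gives 0 to 1.6%. With 11 affected results, 11/225 gives 2.5% to 8.6%.

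**Step 3: post/pre ratio.** If only Day 0 is affected, the ratio is divided by the Day 0 factor. At 5% that is 1/1.070 = 0.935 to 1/1.158 = 0.864, a reduction of 6.5% to 13.6%.

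**Step 4: rules acting downward.** '>' with a bound at or above the cut-off is stored at its lower bound. If k such results have true titres twice the bound (assumed), the GMC factor is 2^(−k/n): 0.994, 0.967 and 0.934 for k = 2, 11 and 22. The two effects can offset each other in the GMC.

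**Step 5: would dropping the results be better?** Let G be the GMC of the unaffected results.

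- *GMC.* Dropping k truly low results inflates it by (G/1.4)^(k/n), against (v/1.4)^(k/n) under the current rule. Dropping is worse whenever G exceeds v, as it would in a high-titre group.
- *Seropositivity.* Let x of the unaffected results be positive. Dropping gives x/(n−k), and the current rule gives (x+k)/n. The numerator difference (x+k)(n−k) − xn equals k(n−x−k), which is never negative. Dropping therefore never overstates seropositivity more than the current rule does.

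**The case against.** The strongest reply is that nothing shows this ELISA ever produces such a string. The SAP says nothing is quantifiable below the cut-off, so the expected low result is '<2.8', which is coded correctly. The conversion list is written for any assay with a cut-off: it covers positive/negative symbols and repeats one line, so the presence of a string in it proves little. The assay description in protocol Appendix A mentions no raised starting dilution or second reporting limit. All of this stands. A reader might infer that the reported rates and GMCs are in fact biased upward. The documents do not support that, because frequency is unknown and the net direction for the GMC also depends on rules that act downward.

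A reader might also give the mirror case equal weight, where '>' with a bound below the cut-off is made seronegative. That case is nearly empty: it needs a lower bound in a range where the SAP says no result is quantifiable.

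Finally, any inflation at Day 0 or in placebo would understate the vaccine response rather than create one. SAP 13.3 treats immunogenicity as descriptive, outside type I error control. That limits the importance but does not remove the defect: a written rule assigns a serostatus that the result does not establish.

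**Conclusion.** The point holds conditionally and is of low priority. As written, SAP 12.2.2 turns an upper-limit result that spans the cut-off into a positive subject with the largest value in the range. If such results occur, seropositivity can be overstated by at most their share of samples, mainly at Day 0 and in placebo. The GMC there can rise by the factors tabulated above, and the post/pre ratio can fall accordingly. These sizes rest on assumed shares and bounds and on every affected titre being truly below 2.8 EU/mL, so they are upper limits. Where the true titre lies between 2.8 and the bound, serostatus is right and the GMC error is smaller. If no such result occurs, the effect is zero. The primary and other efficacy analyses are not touched.

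**What to change.** Amend SAP 12.2.2 and the derivation code as follows.

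1. **Serostatus.** Treat any censored result whose range spans the cut-off as non-evaluable under SAP 12.2.1, unless a retest gives a number. This covers '<' with a bound above the cut-off and '≤' with a bound at or above it. If they ever occur, it also covers '>' or '≥' with a bound below it.
2. **GMC.** Do not simply drop these results, because that removes low titres selectively. Keep the '<' and '≤' results and report the GMC twice, once with them set to half the cut-off and once to the stated bound, so that the effect is visible. For a '>' or '≥' result below the cut-off neither value is an upper limit, so rely on the retest and the count.
3. **Reporting.** Give the number of such results by arm and time point. A count of zero closes the matter.

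The cost is a few lines of derivation code, one extra sensitivity line in the GMC table and possibly a few non-evaluable serostatus values. Excluding truly negative results from the seropositivity denominator can still overstate the rate, but never by more than the current rule does.

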11.9.3. CMI and humoral immune responses

11.9.3.1. M72-specific CD4+/CD8+ T-cells expressing at least two different immune markers (IFN- γ and/or IL-2 and/or TNF- α and/or CD40L)

The following parameters will be tabulated at Days 0, 60 and Years 1, 2 and 3:

- Descriptive statistics of the frequency of M72-specific CD4+/CD8+ T-cells per million cells identified after *in vitro* stimulation expressing at least two different immune markers (IFN- γ and/or IL-2 and/or TNF- α and/or CD40L) after background subtraction for each treatment group.
- A box and whiskers plot of the frequency of M72-specific CD4+/CD8+ T-cells expressing at least two different immune markers (IFN- γ and/or IL-2 and/or TNF- α and/or CD40L) for the M72/AS01_E group.

- Comparison of the frequency of M72-specific CD4+/CD8+ T-cells expressing at least two different immune markers (IFN- γ and/or IL-2 and/or TNF- α and/or CD40L) between PRE and all time points for the M72/AS01_E group.
- Comparison of the frequency of M72-specific CD4+/CD8+ T-cells expressing at least two different immune markers (IFN- γ and/or IL-2 and/or TNF- α and/or CD40L) between PII(D60) and all time points for the M72/AS01_E groups.
- Percentage of responders for M72-specific CD4+/ CD8+ T-cells expressing at least two different immune markers (IFN- γ and/or IL-2 and/or TNF- α and/or CD40L) for treatment group, according to different responder definitions (see Section 12.2.2)

P-value below 5% will be used to identify events that are recognised as worthy of further investigation and such comparisons should be considered as purely exploratory. Such a caution is driven by the problem of unadjustment for multiplicity of tests, potentially a lack of power and that the clinical/biological relevance of the difference is not accounted for.

11.9.3.2. M72-specific CD4+/CD8+ T-cells expressing any combination of immune markers among IFN- γ , TNF- α , IL-2 and CD40L

The following parameters will be tabulated at Days 0, 60 and Years 1, 2 and 3:

- Descriptive statistics of the frequency of M72-specific CD4+/CD8+ T-cells per million cells identified after *in vitro* stimulation expressing any combination of immune markers among CD40L, IFN- γ , IL-2 and TNF- α , after background subtraction for each treatment group.
- A box and whiskers plot of the frequency of M72-specific CD4+/CD8+ T-cells expressing any combination of immune markers among CD40L, IFN- γ , IL-2 and TNF- α , for M72/AS01_E group.

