13.3. Interpretation of analyses

For the analysis of the primary objective, a predefined success criterion and an appropriate type I error control are defined. The confirmatory secondary objective will be analysed only if the primary objective is met. Because of this hierarchy, the type I error is controlled. All other analyses will be descriptive with the aim to characterise the difference in TB incidence, reactogenicity and immunogenicity between groups. These descriptive analyses should not be interpreted.

The triggered primary analysis of efficacy is the analysis where all the alpha is spent.

The sensitivity analysis is for hypothesis generation and thus not confirmatory.

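### For cells with at least two markers, a background-subtracted value of exactly 0 is not floored, so a zero baseline satisfies the 2-, 3- and 4-fold responder rules whatever follows, even 0 to 0

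*SAP*

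**What the plan says.** SAP section 12.2.2 gives two ways to derive the frequency of M72-specific cells with at least two markers. Method 1 works combination by combination ("Background reduction: stimulated minus background value"), replaces a difference below 0 by 1, and then sums. Method 2 sums first, subtracts, and floors once: "Stimulated minus background value. If the difference is < 0 , then the value 1 was given". The choice is stated for one cell type: "The method 2 will be used for the analysis of CD4+ T-cells polypositives". Units are given for both: "ICS data will be expressed as M72-specific CD4+/CD8+ T-cells per million CD4+ or CD8+ T-cells, respectively".

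The same section defines a responder either by exceeding the 95th percentile of baseline values or by a fold rise: "Whose post-vaccination frequency of cells is at least 2 times/at least 3 times/at least 4 times his/her frequency of cells at pre-vaccination". SAP section 11.9.3.1 plans, by treatment group, "Percentage of responders for M72-specific CD4+/ CD8+ T-cells expressing at least two different immune markers", and treats the definitions as alternatives, not as joint conditions.

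For the any-combination ICS data, a few lines further on in section 12.2.2, the floor is worded differently: "Replacement of negative or null value by 1".

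**The concern.** The floor exists so that a fold rise can be computed when there is no signal above background. By catching only strictly negative differences, it misses the plainest case of no signal, a difference of exactly 0. Two things follow. The ordering is reversed: a subject below background gets 1 and a subject exactly at background gets 0. And a zero baseline makes the fold-rise condition empty, because every derived value is at least 0 and any multiple of 0 is 0.

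Subjects with no detectable cells before or after vaccination would then be tabulated as 4-fold responders. Exact zeros arise most readily when neither the stimulated nor the background tube contains a positive cell, so sparse populations are the exposed ones.

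**Working it through.** The plan states no figure for this point, so there is nothing to reproduce. The check applies the rules as written and then again with the any-combination floor.

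**Rules.** Let d be stimulated minus background.
- As written: f(d) = 1 if d < 0, otherwise d.
- Any-combination floor: f(d) = 1 if d ≤ 0, otherwise d.
- Responder at k-fold: f(post) ≥ k·f(pre), for k = 2, 3, 4.

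**Worked cases** (responder at 2/3/4-fold).

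| d pre, d post | As written | Zero also floored |
|---|---|---|
| 0, 0 | 0, 0: yes/yes/yes | 1, 1: no/no/no |
| 0, −50 | 0, 1: yes/yes/yes | 1, 1: no/no/no |
| 0, 300 | 0, 300: yes/yes/yes | 1, 300: yes/yes/yes |
| −50, −50 | 1, 1: no/no/no | 1, 1: no/no/no |
| −50, 3 | 1, 3: yes/yes/no | 1, 3: yes/yes/no |

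Method 1 has the same gap. Four markers give 6 + 4 + 1 = 11 combinations with at least two. All zeros sum to 0; all negatives sum to 11.

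**Size as a function of q.** Let q be the share of zero baselines (an assumption; the documents give none). With no true response and symmetric noise, P(post ≤ 0) = q + (1 − q)/2 = (1 + q)/2. The responders wrongly added are about P(pre = 0) × P(post ≤ 0) = q(1 + q)/2:
- q = 1%: 0.01 × 1.01/2 = 0.5 points
- q = 5%: 0.05 × 1.05/2 = 2.6 points
- q = 10%: 0.10 × 1.10/2 = 5.5 points
- q = 20%: 0.20 × 1.20/2 = 12 points

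With about 225 sub-cohort subjects per group (protocol section 6.2.3), 5.5 points is about 12 subjects.

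**Illustration by simulation.** Assumptions: 1,000,000 subjects per setting; no true response; Poisson counts with mean m per 100,000 cells in both tubes at both visits; cell totals lognormal around 100,000 with a coefficient of variation of 20%, drawn separately for each tube; values per million.

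| m | q | 2-fold responders, as written | 2-fold, zero floored | Gap (points) |
|---|---|---|---|---|
| 0.2 | 67% | 70.1% | 13.6% | 56.5 |
| 0.5 | 37% | 48.5% | 22.3% | 26.2 |
| 1 | 14% | 36.1% | 27.7% | 8.4 |
| 2 | 2% | 31.6% | 30.4% | 1.2 |
| 5 | 0% | 31.4% | 31.4% | 0 |

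The approximation agrees: q = 0.141 gives 0.141 × 1.141/2 = 8.0 points, against 8.4 simulated. At 4-fold the shares are 69.8% vs 13.0% (m = 0.2), 32.2% vs 23.2% (m = 1) and 26.5% vs 26.5% (m = 5). Varying the coefficient of variation from 5% to 40% gives a 2-fold gap of 8.3 to 9.3 points at m = 1, 1.1 to 1.7 at m = 2, and 0 at m = 5. The share above the 95th percentile of baseline was the same under both floors.

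**The case against.** The literal reading is not in dispute. The case against giving it weight has four parts.

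- **Baseline reactivity.** The simulation assumes no M72-reactive cells at all, yet the trial enrols IGRA-positive adults and M72 is built from Mtb antigens. With an assumed constant pre-existing response of 3 cells per 100,000, the 2-fold shares become 24.2% vs 23.9%, 25.7% vs 25.5% and 27.5% vs 27.4% at background means of 0.2, 0.5 and 1. With a response of 1 per 100,000, the gaps are 9.0, 4.9 and 1.9 points. This stands: the large gaps need nearly empty tubes.
- **Which arm.** A zero-baseline subject who truly responds is a responder under either floor. With no baseline response and an assumed rise of 10 per 100,000, the shares are 99.90% vs 99.88% even with 67% zero baselines. This also stands: the artefact mainly raises the placebo percentage, or that of a non-responding population (possibly CD8+), and narrows the contrast between arms.
- **Programming.** Coded as post divided by pre, 0 over 0 is undefined and creates no responder. That does not rescue the rule. The SAP words it as a multiple, and a ratio would leave every zero-baseline subject undefined, true responders included.
- **Peripheral output.** The listed CMI endpoint (SAP section 4.2) is any combination of markers, whose floor is sound. Protocol section 11.8.1.1 plans no responder percentages; only the SAP adds them. SAP section 13.3 says of the descriptive analyses: "These descriptive analyses should not be interpreted". This stands and keeps the point minor.

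**Conclusion.** The rule is wrong as written. For cells with at least two markers, a zero baseline meets all three fold-rise definitions regardless of the later value, and the SAP's other ICS derivation shows that zeros were meant to be handled. The textual gap is certain; its effect is not. It depends on how often exact zeros occur, which the documents do not report, and on how the fold rise is coded. It could be negligible for CD4+ and is potentially visible only where counts are very low and there is little baseline reactivity. The 95th-percentile definition was unaffected in the simulations, and no efficacy analysis uses these values. Severity is minor.

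**What to change.** In Methods 1 and 2 of SAP section 12.2.2, change the condition from less than 0 to less than or equal to 0, so that zero and negative differences both become 1, as in the any-combination derivation. In the same edit, state which method applies to CD8+. Responder percentages are planned for it but Method 2 is assigned to CD4+ only, and the two methods can differ because one floors before summing and the other after.

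The cost is one symbol per method, one clause, and the matching line of derivation code. Only descriptive immunogenicity output changes. The edit removes only the responders created by the zero gap. Responders produced by assay noise remain (27.7% at 2-fold with mean count 1 in the illustration).

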- Descriptive statistics of the frequency of M72-specific CD4+/CD8+ T-cells expressing any combination of immune markers among IFN- γ , TNF- α and IL-2 for each treatment group.
- A box and whiskers plot of the frequency of M72-specific CD4+/CD8+ T-cells expressing any combination of immune markers among IFN- γ , TNF- α and IL-2 for the M72/AS01_E group.
- Descriptive statistics of the frequency of M72-specific CD4+/CD8+ T-cells expressing at least IL-2 for each treatment group (total IL-2).
- Descriptive statistics of the frequency of M72-specific CD4+/CD8+ T-cells expressing at least IFN- γ for each treatment group (total IFN- γ).
- Descriptive statistics of the frequency of M72-specific CD4+/CD8+ T-cells expressing at least TNF- γ for each treatment group (total TNF- α).
- Box and whiskers plots of the frequency of M72-specific CD4+/CD8+ T-cells expressing at least IL-2, at least IFN- γ or at least TNF- α for the M72/AS01_E group.

- Comparison of M72-specific CD4+ cells expressing at least IL-2, at least IFN- γ or at least TNF- α between PRE-and all timepoints for the M72/AS01_E group.
- Comparison of M72-specific CD4+ cells expressing at least IL-2, at least IFN- γ and at least TNF- α between PII(D60) and all timepoints for the M72/AS01_E group.

P-value below 5% will be used to identify events that are recognised as worthy of further investigation and such comparisons should be considered as purely exploratory. Such a caution is driven by the problem of adjustment for multiplicity of tests, potentially a lack of power and that the clinical relevance of the difference is not accounted for.

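### Total IL-2, IFN-γ and TNF-α frequencies are biased upward because SAP 12.2.2 replaces non-positive marker combinations by 1 before summing eight of them

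*SAP*

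**What the plan says.** SAP 12.2.2 gives two derivations for the ICS data.

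**At least two markers.** The section describes two orders. Method 1 subtracts and replaces per combination, then sums. Method 2 starts with "Sum of all the combinations with at least 2 immune markers for the stimulated frequencies", does the same for background, subtracts once, and, if that single difference is below zero, "then the value 1 was given". The choice is stated: "The method 2 will be used for the analysis of CD4+ T-cells polypositives".

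**Any combination of markers.** The steps are listed in this sequence:

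1. subtract background;
2. "Replacement of negative or null value by 1";
3. "Calculation of new combinations of immune markers without the CD40L marker", where the example adds the IL-2-only and the IL-2/CD40L terms;
4. form the per-marker totals: "The frequency of M72-specific CD4+/CD8+ T-cells expressing at least a given immune marker represents the sum of single, double, triple, quadruple positive". The IL-2 example lists eight terms.

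SAP 11.9.3.2 tabulates the three totals for CD4+ and CD8+ cells, by treatment group, at Day 0, Day 60 and the three yearly visits. It plots them for the M72/AS01E group and compares CD4+ totals over time in that group. No correction or footnote for the replacement step is planned.

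**The concern.** Replacing each term before adding discards negative noise and keeps positive noise. A combination with no true signal therefore contributes a positive amount on average, and each total collects up to eight such contributions. In groups or visits with little response, part of the tabulated level would come from the derivation and not from cells. The same section already contains the order that avoids most of this, and uses it for CD4+ polypositive cells. No reason is given for doing otherwise with the totals. What is at stake is the reading of low descriptive levels.

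**Working it through.** The SAP gives no figure of its own here, so there is nothing to reproduce.

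**Inputs from the documents.** The step order and the replacement rule are in SAP 12.2.2, as is the unit (cells per million CD4+ or CD8+ T-cells). The listed steps are read as sequential and as acting on individual combinations, since step 3 builds new combinations from the result.

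**Number of terms.** Four markers give 2^4 − 1 = 15 positive combinations. Those containing IL-2 number 2^3 = 8 (1 single, 3 double, 3 triple, 1 quadruple), and likewise for IFN-γ and TNF-α.

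**Direction, with no assumption.** A zero is raised by 1 and a negative difference d by 1 + |d|. A positive value is unchanged, even below 1. Each total is therefore at or above its raw sum. If all eight differences are zero or negative, the total is 8 × 1 = 8, against 1 if summed first and replaced once under the same rule. A CD40L-merged combination has two terms, so the corresponding values are 2 and 1.

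**Size, under an assumption.** Let the background-subtracted noise per combination be independent and normal with SD s per million. The documents do not give s, so a range is shown. With no true response:

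- SAP order, mean total = 8 × (s/√(2π) + 0.5) = 8 × (0.399s + 0.5)
- summed first, mean total = 0.399 × s√8 + 0.5 = 1.128s + 0.5

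| s (per million) | SAP order, mean | SAP order, median (simulated) | Summed first, mean | Summed first, median |
|---|---|---|---|---|
| 2 | 10.4 | 10 | 2.8 | 1 |
| 5 | 20 | 19 | 6 | 1 |
| 10 | 36 | 34 | 12 | 1 |
| 20 | 68 | 64 | 23 | 1 |
| 50 | 164 | 155 | 57 | 1 |

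For one CD40L-merged combination at s = 10, the means are 2 × (3.99 + 0.5) = 9.0 and 0.399 × 10√2 + 0.5 = 6.1.

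**Count-based check.** This uses Poisson counts with 50,000 to 200,000 cells and background of 5 to 50 per million per combination, all assumed, and no response. The mean total is 26 to 144 in the SAP order against 9 to 51 summed first; the median is 25 to 143 against 1. With much lower background (0.1 to 1 per million) the SAP-order mean falls to 8.6 to 15.3.

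**With a true response, s = 10.** If the signal is spread over all eight combinations, the mean offset in the SAP order is about +15 at a true total of 50, +0.5 at 200 and nil at 1000. If only three of the eight respond, it stays near +22 at both 200 and 1000, which is 11% and 2%. Summed first, the median at a true total of 50 is 50 and the mean 50.5.

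**The case against.** - **No decision depends on these outputs.** The per-marker totals are not among the CMI analyses in Protocol 11.8.1.1; the SAP added them (Section 14). SAP 11.9.3.2 calls the comparisons exploratory, and SAP 13.3 says descriptive analyses are not to be interpreted. This stands and sets the priority.

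- **The size is assumed throughout.** This also stands. The documents give no ICS noise, cell counts or background. The largest figures need a true total of zero, yet every participant is IGRA-positive (Protocol 5.2) and M72 comes from two Mtb antigens (Protocol 1.1), so some baseline response is plausible. Only the direction, and the 8-against-1 case, follow from the text.

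- **Additivity.** The SAP defines a total as the sum of its parts. Summing first breaks that for individually replaced parts. This is a real cost, which a footnote can meet.

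- **Before/after comparisons.** A reader might infer that the SAP order weakens the rise from pre- to post-vaccination and that summing first would repair it. The documents do not support this. For an assumed rise from 0 to 300 at s = 20, the SAP order gives a mean difference of 291, 283, 275, 266 and 234 when 1, 2, 3, 4 and 8 combinations respond; summing first gives 277 in every case. Mean/SD of the difference is 6.0, 5.6, 5.1, 4.8 and 3.7, against about 4.2 summed first and 3.75 with no replacement. The SAP does not fix the scale of the comparison. On a ratio scale, a null sum set to 1 is unstable: in this scenario the SD of the log10 ratio is 0.82 summed first, against about 0.25 in the SAP order. How many combinations respond is not stated, so neither order is shown to be better.

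- **Comparison with polypositive cells.** A reader might also infer that one quantity is reported on two scales. That overstates it. Both are per million, and they are different quantities: polypositive cells exclude IL-2-only cells and include combinations without IL-2. They sit in separate subsections, and no comparison between them is planned.

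**Conclusion.** The point holds for the descriptive levels. As listed, the SAP steps can only push the three totals, and the CD40L-merged combinations, upward, and the relative effect is greatest at low totals. The direction rests on the text alone, read as sequential steps. The magnitude rests on assumed independent noise: a null median of about 10 to 155 per million for s from 2 to 50, against 1 when summed first. Whether placebo and Day 0 totals are low enough for this to matter is not known from the documents. Summing first does not remove all bias, because one replacement still leaves a smaller upward shift in the mean (2.8 to 57 over the same range of s with no response).

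Efficacy, alpha, sample size and the at-least-two-marker responder rates are untouched. This is a cheap, low-priority correction.

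**What to change.** In SAP 12.2.2, for the descriptive levels of total IL-2, IFN-γ and TNF-α and of the CD40L-merged combinations (CD4+ and CD8+), sum the stimulated frequencies, sum the background frequencies, subtract once and replace once, as Method 2 does. State one replacement trigger for the whole section; at present one derivation acts on values below zero and the other also on zero. Footnote the tables to say that individually replaced combinations will not add up to the totals.

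A different method for the pre- versus post-vaccination comparisons, including totals with no replacement, is optional. If it is adopted, the scale should be stated.

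The cost is a few lines of derivation code, a short wording change and the footnote. No new data are needed.
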